2.1.3 Safety

2.1.3.1 Adverse events (AEs)

This study focused on the serious adverse events (SAEs) and Adverse Events of Special Interest (AESIs), and all reported SAEs will be blindly reviewed by an independent Adverse Event Committee.

All SAEs and AESIs will be coded using MedDRA 22.0 or higher, before database lock. MedDRA System Organ Class (SOC) and Preferred Term (PT) will be summarized.

Classification of serious adverse events

All SAEs will be classified as follows,

- Death
- Symptomatic intracranial hemorrhage
- De novo Ischemic Stroke
- Large or malignant middle cerebral artery (MCA) infarction

- Pneumonia (Aspiration and others)
- Contrast allergic reaction
- Major bleeding due to femoral artery access complications including groin hematoma, retroperitoneal hematoma
- Acute kidney injury
- Others

Adverse Events of Special Interest

Adverse events of special interest for this study include aspiration pneumonia and allergic contrast reactions.

2.1.3.2 Laboratory variables

Baseline laboratory tests will be conducted at screening visit, which include blood glucose (mmol/L), prothrombin time (sec), international standardized ratio, platelet count ($\times 10^9$), serum creatinine (umol/L).

2.1.3.3 Vital signs

At screening visit, the following vital signs will be measured: systolic blood pressure (mmHg), diastolic blood pressure (mmHg), heart rate (beat/min), body temperature ($^{\circ}\text{C}$), height (cm), weight (kg).

2.1.3.4 Neuroimaging

CT and CTA will be performed at baseline and follow-up visit and the findings of which will be blindly evaluated by an independent Imaging Committee (Core lab), including hyperdense, the Alberta Stroke Program Early CT Score (ASPECTS), another occlusion location of anterior circulation except target lesion, anterior communicating artery (AComA), intracranial hemorrhages ([Table 7 in Appendix](#)), midline shift present, target vessel stent placement, modified arterial occlusive lesion classification (mAOL, ([Table 8 in Appendix](#))), vascular occlusion, etc.

The newly affected territory of the middle cerebral artery was graded by the systematic quantitative scoring system, e.g. ASPECTS. It will be performed at baseline visit and follow-up visit. ASPECTS is allotted 10 points, including caudate, lentiform, internal capsule, insular cortex, M1, M2, M3, M4, M5, M6. One point is subtracted for an area of early ischaemic change, such as focal swelling, or parenchymal hypoattenuation, for each of the defined regions. A score of 0 indicates diffuse ischaemia throughout the territory of the middle cerebral artery.

2.1.4 Health economics

None.

2.2 STATISTICAL ANALYSIS POPULATION

The analysis populations include intention-to-treat population (ITT) and per-protocol set (PPS) for this study.

2.2.1 Intention-to-treat population

All subjects who were randomized will be included in the intention-to-treat population (ITT) according to intention-to-treat principles, in which subjects will be analyzed according to the group assigned by randomization. ITT is the primary efficacy analysis set for this study.

2.2.2 Per-protocol set

Per-protocol set (PPS) is a subset of ITT, including all randomized subjects who have been treated in the study without major protocol deviations that may significantly impact the interpretation of efficacy results. Detailed protocol deviation criteria will be determined at the latest before database lock. PPS will be used for the primary efficacy outcome and safety analysis. Subjects entering PPS need to satisfy all the following basic criteria:

- (1) Meet all the eligibility criteria specified in the study protocol;
- (2) The subjects were randomized and received the assigned treatment, i.e.
 - No IVT was administered before the intended endovascular treatment (EVT) in the intervention group (direct IAT group);
 - IVT was administered before the intended EVT in patients in the control group.
- (3) Underwent groin puncture, with exception of patients with clinical recovery precluding EVT (due to presumed recanalization before mechanical thrombectomy).

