1.2 STUDY OBJECTIVES

The primary objective of this trial is to assess the effect of direct IAT compared with IVT followed by IAT, on functional outcome in patients with acute ischemic stroke (AIS), caused by an anterior circulation occlusion that is confirmed by Computed tomography angiography (CTA).

The secondary objective is to explore for superiority of direct IAT relative to IVT followed by IAT.

The tertiary objective is to assess the effect of direct IAT compared with IVT with IAT on neurological recovery (NIHSS), infarct size and occurrence of Symptomatic intracerebral hemorrhage (sICH).

The fourth objective is to collect thrombi and to analyze them with respect to their potential for treatment effect modification.

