2.3.2 Analysis of efficacy outcomes

All efficacy data analyses will be based on ITT and for primary endpoint PPS will also be used.

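### The per-protocol set keeps unpunctured patients who recovered but excludes those who deteriorated, bled or died, so membership depends on the course after randomisation, and the safety tables inherit that selection

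*SAP*

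**What the plan says.** SAP section 2.2.2 lists three conditions and says "Subjects entering PPS need to satisfy all the following basic criteria". The first is eligibility. The second is receipt of the assigned sequence: no alteplase before the intended EVT in the direct arm, alteplase before it in the control arm. The third is "Underwent groin puncture, with exception of patients with clinical recovery precluding EVT (due to presumed recanalization before mechanical thrombectomy". The wording is the same for both arms. The section adds "Detailed protocol deviation criteria will be determined at the latest before database lock".

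The set has two uses. For efficacy, section 2.2.1 states "ITT is the primary efficacy analysis set for this study", and section 2.3.2 states "All efficacy data analyses will be based on ITT and for primary endpoint PPS will also be used". For safety, section 2.2.2 says "PPS will be used for the primary efficacy outcome and safety analysis", and section 2.3.4 places every safety analysis on the PPS.

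**The concern.** Take two control patients who both receive the assigned alteplase. One recovers and is not punctured; the other bleeds, deteriorates or dies and is not punctured. Both meet criteria (1) and (2), and in both the clinical course is why EVT did not happen. The first stays in the PPS and the second leaves. The SAP does not list the adverse cases by name; their exclusion follows from there being a single exception and from all criteria being mandatory. The deviation criteria still to be written do not cure this, because adding criteria cannot readmit someone who fails a basic one.

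Two things are at stake. The PPS is the only alternative population for the primary endpoint, and in a non-inferiority trial readers look for agreement between ITT and per-protocol results. A selection rule tied to outcome can create or hide disagreement by itself. Second, symptomatic intracranial haemorrhage and death are listed SAE classes (section 2.1.3.1), yet when they occur before puncture and prevent it, the patient is outside the only set used for safety.

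**Working it through.** **1. The plan's own figure.** Section 1.4 gives control mRS 0-6 as 3, 9, 21, 18, 22, 6 and 21%, a cOR of 1.163, a margin of 0.8, 80% power and two-sided alpha of 0.05, leading to 710 and then 636. Whitehead's formula is N = 12(z0.975 + z0.80)² / [ln(1.163/0.8)² × (1 − Σp̄³)], with p̄ the mean of the two arms' distributions. Here (1.960 + 0.842)² = 7.849, ln(1.163/0.8) = 0.3741 and 1 − Σp̄³ = 0.9647, so N = 94.19 / (0.1400 × 0.9647) ≈ 697. A 5,000-run simulation at 710 gives 81.1% power. Then 710 × 0.85 = 603.5, and 603.5 / 0.95 ≈ 636. The figure reproduces, so the same model can be used to size the PPS rule.

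**2. Assumptions for the PPS rule.** The SAP gives no rate of non-puncture for either arm. Assumed: adverse non-puncture of 1-5% per arm, with mRS 4/5/6 in proportions 15/15/70%. On 318 per arm, 1%, 2%, 3% and 5% are about 3, 6, 10 and 16 patients. The direct arm is generated from the control distribution under proportional odds, the adverse unpunctured patients are removed as criterion (3) requires, and an unadjusted proportional-odds model is fitted to the expected counts. P(NI) is the chance that the lower 95% limit exceeds 0.8.

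| Adverse loss, direct / control | PPS cOR, true 1.0 | PPS cOR, true 1.163 | P(NI), true 1.163 | P(NI), true 0.8 |
|---|---|---|---|---|
| none (all kept) | 1.000 | 1.163 | 76% | 2.5% |
| 1% / 1% | 1.000 | 1.165 | 76% | 2.4% |
| 3% / 3% | 1.000 | 1.170 | 76% | 2.2% |
| 1% / 2% | 0.979 | 1.141 | 71% | 1.6% |
| 1% / 3% | 0.958 | 1.117 | 66% | 1.1% |
| 1% / 5% | 0.916 | 1.069 | 53% | 0.4% |
| 2% / 1% | 1.022 | 1.192 | 81% | 3.3% |
| 3% / 1% | 1.044 | 1.221 | 85% | 4.4% |

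The 76% in the first row is below 80% because this is an unadjusted analysis of 636 patients, without the covariate gain that section 1.4 relies on.

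**3. Sensitivity to the assumed mRS.** With the removed patients split 20/80% over mRS 5 and 6, 1% / 2% gives 0.977 and 1% / 3% gives 0.953 at a true cOR of 1.0. Losses of 1%, 2% and 3% in controls only, with none in the direct arm, give 0.977, 0.954 and 0.932.

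**4. Against sampling error.** The standard error of the log cOR is about √[12 / (636 × 0.964)] = 0.140. The shift to 0.979 is ln(0.979) = −0.021, about 0.15 SE; to 0.958 it is −0.043, about 0.3 SE; to 0.916 it is −0.088, about 0.6 SE.

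**5. Dropping every unpunctured patient is not neutral either.** Suppose recovery without puncture occurs in 1% direct and 3% control (assumed mRS 0-6: 30/35/20/10/3/1/1%), with adverse losses of 1% / 2% and a true cOR of 1.0. Keeping all gives 1.000, the SAP rule 0.979, and dropping all 1.024. Only keeping both kinds leaves the estimate where it was.

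**The case against.** The strongest reply is that the rule reads the same for both arms and no direction of bias follows from it alone. That stands. A reader might infer that the PPS flatters the alteplase arm. This needs more adverse non-puncture among controls, and the SAP gives no rates. Section 1.1 sends the direct arm to immediate IAT while controls receive alteplase first, which makes that direction plausible. But direct-arm patients can also worsen between randomisation and puncture, an interval that section 2.3.2.3 treats as a subgroup factor for the whole trial. Equal rates remove the arm bias, and reversed rates favour direct MT.

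A reader might also infer that the PPS is the only support for the non-inferiority conclusion, or that the conclusion itself is at risk. Neither is supported. Section 2.3.2.1 reports an unadjusted estimate beside the adjusted one, ITT keeps every unpunctured patient, and no rule requires the PPS to clear 0.8. If the likely direction is right, the PPS is conservative for direct MT.

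It can further be argued that the exception has a rationale: after presumed recanalisation the target of EVT has gone, whereas a patient who dies before puncture never received the full sequence. This explains why recovery was singled out. It does not remove the dependence on outcome, since the recovered patient did not receive the full sequence either.

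Section 2.2.3 will count patients randomised, treated and analysed, which helps, but it does not promise reasons for non-puncture by arm. On safety, death within 90 days is also a secondary efficacy variable and so is analysed on ITT. Haemorrhage and the SAE tables have no such backup.

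**Conclusion.** The point holds as a defect in the definition of a supporting analysis set. Criterion (3) selects on a post-randomisation course that predicts the 90-day mRS. The effect on the PPS cOR is nil at equal adverse losses when the true cOR is 1.0, and small for plausible imbalances: about 0.98-0.95 for 1% direct against 2-3% control, or 0.15 to roughly 0.3 SE. At the design cOR of 1.163, the same imbalances cut the chance that the PPS meets the margin from 76% to 71% or 66%. Bias against direct MT is likely but not established. If the imbalance ran the other way, false non-inferiority in the PPS at a true cOR of 0.8 would rise from 2.5% to 3.3-4.4%. All these sizes rest on assumed non-puncture rates and an assumed mRS for the excluded patients.

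The heavier consequence needs no such assumption: with safety placed wholly on the PPS, a bleed or death that prevents puncture is not counted in the safety tables.

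**What to change.** Before database lock:

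- Reword criterion (3) so that a patient who met criteria (1) and (2) is kept if punctured, or if not punctured because of the clinical course after randomisation, whether recovery, deterioration, haemorrhage or death. Exclusion under this criterion is then confined to non-clinical reasons, such as refusal or logistics.
- Tabulate non-puncture by arm and reason.
- In sections 2.2.2 and 2.3.4, base the safety analyses on all randomised or all treated patients, with the PPS at most as a supplement.

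This changes analysis-set definitions only and leaves patient management alone. The cost is a few sentences in the SAP and one extra table. The downside is that the PPS will hold a few more unpunctured patients and move slightly towards ITT, which the SAP already accepts for recovered patients.

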2.2.3 Subject disposition

The number and proportion of screened, randomized, treated and analyzed subjects will be provided. Where necessary, the CONSORT flow chart will be presented to describe the subject disposition in the statistical analysis report.

2.3 STATISTICAL METHODS

For normally distributed continuous data, the following statistics will be provided: number, mean, standard deviation (SD), minimum and maximum. For non-normally distributed continuous data, number, median, lower quartile (Q1), upper quartile (Q3) will be provided, unless otherwise stated. Categorical data will be summarized in terms of the number of patients and percentages.

For summary statistics, mean, standard deviation, median and quartiles will be reported to 1 more decimal place than the original data, while the 95% confidence interval (CI) will be reported to 2. Minimum and maximum values will be reported to the same number of significant digits as the original data. In the frequency table, the percentages will keep 1 decimal, the p values keep 4 decimal or displayed as "<0.0001".

2.3.1 Demography and baseline characteristics

Demography and baseline characteristics will be statistically summarized by treatment group.

In addition, the medical history, smoking history, drug treatment history and other information will be summarized. Data listings will be provided where necessary.

2.3.2 Analysis of efficacy outcomes

All efficacy data analyses will be based on ITT and for primary endpoint PPS will also be used.

2.3.2.1 Primary efficacy outcome

The primary effect parameter is the common odds ratio, which will be estimated by ordinal logistic regression (proportional odds model), which represent the shift on the full distribution of the modified Rankin Scale at 90±14 days. Estimations will be adjusted by known prognostic variables such as age (median), pre-stroke mRS (continuous), time from symptom onset to randomization (" \leq Q1", ">Q1, \leq Q2", ">Q2, \leq Q3", ">Q3"), stroke severity (NIHSS, median) and collaterals (Grade 0-1, Grade 2-3). Adjusted and unadjusted estimations and their corresponding 95% confidence intervals will be reported. To assess non-inferiority of direct MT compared to IVT with MT, we will assess whether the 95% CI lower bound of the adjusted common odds ratio cross our pre-specified non-inferiority boundary (0.8).

The following SAS procedure will be used for ordered logistic regression analysis (proportional odds model):

```
Proc logistic data=XXX;  
Class TRT FactorA ...;  
Model mRS90= TRT AGE FactorA ...;
```

Run;

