1.4 SAMPLE SIZE CALCULATION

We based our estimations on the distribution of the mRS in the control group of the trial, which we derived from the intervention group of the MR CLEAN trial [3]: mRS 0: 3%; mRS 1: 9%; mRS 2: 21%; mRS 3: 18%; mRS 4: 22%; mRS 5: 6% and mRS 6: 21%. We assumed a favorable treatment effect with a common odds ratio (cOR) of 1.163, corresponding to a 4% absolute increase in the rate of mRS scores of 0-2. The main purpose is to demonstrate non-inferiority, that is, the lower limit of the two-side 95% confidence interval does not cross the pre-specified cOR non-inferiority Cutoff of 0.8. In a simulation with 5000 runs we computed the proportion of positive trials, for a given sample size. A sample size of 710 was determined to detect the pre-defined non-

inferiority with a power of 80% and two-sided alpha of 0.05. Using covariate adjustment with at most 25%, a conservative 15% sample size reduction can be achieved, plus 5% dropout rate, leading to a final sample size of 636, 318 per arm.

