2.1.2.2 Secondary efficacy variables

- Death within 90 days (± 14 days)
- Pre-interventional recanalization
- eTICI score on final angiography of IAT. ([Table 2 in Appendix](#))
- Recanalization rate at 24-72 hours, assessed with CTA
- Score on the NIHSS at 24 \pm 6 hours and 5 -7 days. ([Table 3 in Appendix](#))
- Final infarct volume at 5-7 days. Final infarct volume will be assessed with the use of an automated, validated algorithm. Infarct size at day 5-7 will be compared with plain CT and perfusion CT results (if available) at baseline.
- Dichotomized mRS of 0-1 vs. 2-6 at 90 days (± 14 days)
- Dichotomized mRS of 0-2 vs. 3-6 at 90 days (± 14 days)
- Dichotomized mRS of 0-3 vs. 4-6 at 90 days (± 14 days)
- Dichotomized mRS of 0-4 vs. 5-6 at 90 days (± 14 days)
- Dichotomized mRS of 0-5 vs. 6 at 90 days (± 14 days)

- Score on the EQ5D-5L and Barthel index at 90 days (± 14 days)

Pre-interventional recanalization: Recanalization rate (eTICI 2b, 2c or 3) before patients received mechanical intra-arterial treatment according to the DSA.

Recanalization rate at 24-72 hours: defined as the proportion of patients in whom recanalization as determined on 24-72 hours CTA is achieved.

eTICI score: eTICI assessment will be performed post IAT. The eTICI classification includes 0, 1, 2a, 2b, 2c and 3 ([Table 2 in Appendix](#)).

NIHSS score: The NIHSS is an ordinal hierarchical scale to evaluate the severity of stroke by assessing a patient's performance. Scores range from 0 to 42, with higher scores indicating a more severe deficit ([Table 3 in Appendix](#)). NIHSS assessment will be performed at baseline, 24 ± 6 hours post operation and 5-7 days post operation.

The EuroQoL 5-dimensions 5-level (EQ-5D-5L) questionnaire is a standardized measure of health outcome that has been used extensively in patients with stroke ([Table 5 in Appendix](#)). EQ5D-5L assessment will be performed at 90 ± 14 days post operation.

The Barthel index (BI) is an ordinal scale used to measure performance in 10 activities of daily living (ADL). Test scores range from 0 to 100, with higher scores indicating better performance in these daily activities ([Table 4 in Appendix](#)). BI assessment will be performed at 90 ± 14 days post operation.

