2.3.2.2 Secondary efficacy outcome

Continuous secondary efficacy outcomes are mainly infarct size at 5-7 days after operation and recanalization rate before intervention as well. Analysis for these outcomes will be mainly based on statistical descriptions. Where necessary, analysis of variance or corresponding non-parametric test will be used for between-group comparisons. If applicable, the linear regression analysis will be used with adjustment for the same covariate variables as the primary outcome analysis. When deemed necessary, log or other common transformation of non-normal distribution will be used.

Categorical secondary outcomes include mortality at 90 days after operation, recanalization rate at 24-72 hours, dichotomized mRS score at 90 days after operation (0-1 vs. 2-6, 0-2 vs. 3-6, 0-3 vs. 4-6), successful recanalization before and after Mechanical thrombectomy (MT), and eTICI score at MT final angiography. Chi-square test will be used for comparison between the two groups, or Fisher's exact test will be used for comparison when applicable. The categorical secondary outcomes will be analyzed by logistic or ordered regression analysis to provide a common odds ratio and its confidence interval, if applicable. The adjustment method is the same as that in the primary outcome analysis.

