2.3.5 Analysis of quality of life

2.3.5.1 NIHSS score

NIHSS (0-42) score and change from baseline are continuous variables and will be presented with summary statistics, including number of subjects, mean, standard deviation, median, minimum and maximum, by treatment groups and by visits. Repeated measures of variance analysis will be used to explore the impact of treatment grouping visits and NIHSS baseline levels.

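### The primary non-inferiority model appears to cut age and baseline NIHSS at the median; using the full values already collected costs almost nothing, probably gains a little power, and removes an unstated tie rule

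*SAP*

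**What the plan says.** SAP section 2.3.2.1 compares the lower limit of the 95% confidence interval of the adjusted cOR with 0.8. The adjustment is set out in one sentence: "Estimations will be adjusted by known prognostic variables such as age (median), pre-stroke mRS (continuous), time from symptom onset to randomization", the last in four quartile classes, followed by "stroke severity (NIHSS, median) and collaterals (Grade 0-1, Grade 2-3").

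Each bracket in that sentence states a coding: continuous for pre-stroke mRS, four classes for time, two grades for collaterals, and *median* for age and for NIHSS. Read alongside the others, *median* means two levels, cut at the sample median. The sentence does not say in which analysis set the median is taken or on which side a patient at the median falls. The words *such as* leave the list of covariates open.

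Both variables are available uncut: Table 1 in section 1.5.1 lists age and every NIHSS item. Section 2.3.2.2 carries the model over to the categorical secondary outcomes: "The adjustment method is the same as that in the primary outcome analysis". Section 1.4 relies on the adjustment for the size of the trial: "Using covariate adjustment with at most 25%, a conservative 15% sample size reduction can be achieved".

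**The concern.** Cutting a graded prognostic variable in two treats everyone on one side of the cut as equal. The part of the outcome variation that age and stroke severity could still explain within each half is left in the residual, which weakens the adjustment. That matters more than usual here because patients were traded for adjustment.

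A cut also creates a boundary. Age in years and NIHSS are whole numbers, so several patients will usually sit exactly on the median, and the plan does not place them. A verdict resting on one confidence limit can depend on such a detail.

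**Working it through.** **The plan's own figures.** Inputs from section 1.4: control mRS 3/9/21/18/22/6/21%, cOR 1.163, margin 0.8, power 80%, two-sided alpha 0.05. The proportional-odds formula is N = 12(z0.975 + z0.80)² / [ln(1.163/0.8)² × (1 − Σp̄³)], where p̄ is the mean category probability over the two arms. It gives 697, against 710 from the plan's simulation (1.8% apart). Then 710 × 0.85 = 603.5, and 603.5/0.95 = 635.3, rounded up to 636 as stated. The analysed number is therefore about 604.

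**Information kept by a split.** For a normal covariate, the correlation between the value and its median indicator is 0.399/0.5 = 0.798. Its square is 0.637, so 64% of the variance is kept and 36% lost.

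**Power.** The SAP gives no covariate strengths, so four sets of log-odds are assumed:

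| | weak | lower-moderate | moderate | strong |
|---|---|---|---|---|
| age, per SD | 0.25 | 0.42 | 0.45 | 0.60 |
| NIHSS, per SD | 0.30 | 0.48 | 0.60 | 0.80 |
| time, per SD | 0.05 | 0.10 | 0.10 | 0.15 |
| collaterals, per grade | 0.15 | 0.30 | 0.30 | 0.45 |
| pre-stroke mRS, per point | 0.20 | 0.35 | 0.35 | 0.50 |

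The age-NIHSS correlation is set at 0.1. Proportional-odds models were fitted to exact outcome probabilities calibrated to the section 1.4 distribution, with standard errors scaled to 604 patients and a one-sided 0.025 test against 0.8. Both models hold time, collaterals and pre-stroke mRS as the SAP codes them; only age and NIHSS differ.

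| Power, % | weak | lower-moderate | moderate | strong |
|---|---|---|---|---|
| conditional cOR 1.163, split | 73.5 | 72.5 | 72.1 | 70.7 |
| conditional cOR 1.163, uncut | 73.8 | 73.3 | 73.1 | 72.2 |
| gain | 0.3 | 0.8 | 1.0 | 1.5 |
| marginal cOR 1.163, split | 74.8 | 76.0 | 76.4 | 77.9 |
| marginal cOR 1.163, uncut | 75.1 | 76.7 | 77.4 | 79.6 |
| gain | 0.3 | 0.7 | 1.0 | 1.7 |

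In the conditional case the loss is worth about 4/10/14/22 of the 604 patients. For scale, the 15% reduction removed 710 − 603.5 = 106.5.

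A separate simulation (8,000 trials per cell, 604 patients, conditional cOR 1.163) gave age and NIHSS the same log-odds per SD: 0.25, 0.45 and 0.70. Power was 72.2/71.5/69.6% split and 72.5/72.6/71.5% uncut, a gain of 0.4/1.1/1.9 points. At 0.90 per SD the gain was 2.1.

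**Opposite verdicts.** Each simulated trial in that same run was analysed both ways:

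| Opposite verdicts, % | 0.25 | 0.45 | 0.70 |
|---|---|---|---|
| true cOR 1.163 | 3.5 | 6.0 | 9.2 |
| true cOR 1.0 | 4.1 | 6.6 | 10.1 |
| true cOR 0.8 | 0.6 | 1.3 | 1.9 |

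At 0.90 per SD these become 11.7, 12.3 and 2.7%. At cOR 1.163 only the split passed in 1.6/2.4/3.7% of trials, and only the uncut model in 2.0/3.6/5.6%. Simulating the four sets in the first table (5,000 trials each, cOR 1.163) gave 3.5/5.9/6.8/10.0% in total.

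**Tie rule.** Keeping the split and changing only > to >= at the median altered 2.2 to 6.1% of verdicts at cOR 1.0 to 1.163, for log-odds 0.25 to 0.70.

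**Shape of the effect.** If the true effect were a pure step at the median, linear terms would lose 0.3/0.8/1.0/1.7 points over the four sets. If it were flat below the median and rising above it, they would still gain 0.3/0.5/0.6/0.9.

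**The case against.** The strongest objection is that the plan has already chosen. Every bracket is a coding, so an analyst following the SAP would split, and the disagreement rate merely compares two different models. This stands: the 3.5 to 10% shows that the choice has consequences, not that the plan's choice is wrong.

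A second objection is that the power gain assumes roughly linear effects and reverses under a step. That also stands, though a step located exactly at the sample median is a special case.

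A third is that confirming the split and adding a tie rule would be enough. That would close the gap in definition, but would still leave collected information unused.

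A reader might infer two stronger points that the SAP does not support.

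- *That the SAP contradicts itself on the coding.* The template lines "Class TRT FactorA" and "Model mRS90= TRT AGE FactorA" are placeholders, and a two-level age variable gives the same treatment estimate inside or outside CLASS. "The NIHSS is an ordinal hierarchical scale to evaluate the severity of stroke" and "NIHSS (0-42) score and change from baseline are continuous variables" describe NIHSS as an outcome score. The three-level groups in Appendix Table 10 are for subgroups.
- *That the split inflates false non-inferiority.* At a conditional cOR of 0.80 (four assumed sets), the one-sided error is 2.6/2.8/2.9/3.2% split and 2.5/2.5/2.5/2.6% uncut. At a marginal 0.80, both are below 2.5%: 2.3/1.9/1.8/1.4% and 2.2/1.7/1.5/1.1%. Coarser adjustment pulls the odds ratio towards 1, so the two codings estimate slightly different quantities. With the split model's own cOR at about 0.8, its error was 2.7% (log-odds 0.45) and 2.9% (0.70), with a simulation standard error of √(0.025 × 0.975/8000), about 0.2 points. No general inflation is claimed.

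**Conclusion.** The point holds as an inexpensive improvement to a legitimate primary model, together with a small gap in its definition. It should be made, but the trial's validity does not depend on it.

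The likely cost of the split is small, and its exact size is uncertain because the covariate strengths are assumed and linearity favours the uncut model. The missing tie rule does not depend on linearity: even an analyst who accepts the split must make a choice that the SAP leaves open and that can occasionally decide the result. The verdict-change rates should always be quoted with the true cOR, since they fall sharply at the margin. Whether adjustment can deliver the 15% sample-size reduction is a separate question, not judged here.

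**What to change.** In section 2.3.2.1, before database lock:

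1. Replace *such as* with a closed list: age in years (continuous, linear), baseline NIHSS total 0-42 (continuous, linear), and pre-stroke mRS, onset-to-randomization time and collaterals exactly as coded now.
2. Complete the template to match, for example `Class TRT TIMEQ COLLAT;` and `Model mRS90 = TRT AGE NIHSS PREMRS TIMEQ COLLAT;`.
3. Keep the median-split model as a sensitivity analysis, stating the cut-point, the analysis set in which the median is taken, and whether patients at the median go to the upper or lower group.

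The cost is one sentence and two lines of code, with no further data or patients. The downside is the linearity assumption for age and NIHSS; a spline version could be added as a further sensitivity analysis. If the sponsor prefers to keep the split as primary, the details in step 3 and a closed list are the minimum needed.
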